5.1 Primary Endpoint(s)

Placebo-corrected changes in peak VO₂ at CPX after 24 weeks of treatment will be considered the primary endpoint. This will compare patients treated with anakinra (N=68) vs placebo (N=34), and provide a randomized, double-blinded assessment of the effects of IL-1 blockade on aerobic exercise performance. The data will be collected and electronically transferred to the core laboratory at the University of Illinois, Chicago, IL ([name]).

5.2 Secondary Exploratory Endpoints

Secondary exploratory endpoints will include parameters measured at CPX, echocardiography, non-invasive hemodynamics, as well as biomarkers, and clinical outcomes.

Additional CPX parameters: secondary endpoints include changes in peak VO₂ at earlier endpoints (6 and 12 weeks), and changes in other CPX variables such as ventilatory efficiency (ventilation-carbon dioxide elimination slope [VE/VCO₂ slope]) and oxygen utilization efficiency slope [OUES]), anaerobic threshold, and peak oxygen pulse at 6, 12, and 24 weeks.

Echocardiography: secondary endpoints include measuring left ventricular end-diastolic and end-systolic volumes, ejection fraction, stroke volume estimated by left ventricular outflow tract velocity-time integral, measures of myocardial relaxation at tissue Doppler E', and estimate of left ventricular filling pressure using E/E' ratio at baseline, 6, 12 and at 24 weeks.

Non-invasive hemodynamics: secondary endpoints include estimates of arterial elastance (E_a), a measure of afterload, end-systolic elastance (E_{es}), a measure of load-independent contractility also defined as end-systolic pressure-volume relationship,

ventriculo-arterial coupling is defined as the ratio of E_a to E_{es} , at 6, 12 and 24 weeks. The hemodynamic assessment will be conducted with echocardiography and non-invasive blood pressure measuring.

Quality of life assessment: the Duke Activity Status Index (DASI), the Kansas City Cardiomyopathy Questionnaire (KCCQ), the International Physical Activity questionnaire (IPAQ-SF) and the Patient Health Questionnaire-9 (PHQ-9) will be administered at baseline, 6, 12 and 24 weeks to assess patient perception of changes.

Biomarkers: Blood will be collected at each visit (baseline, 6, 12, and 24 weeks) and analyzed for a panel of complete blood cell count with differential, basic metabolic panel, high sensitivity C- reactive protein (CRP), and NT-proBNP. In addition, 5 – 10mL of blood will be stored frozen for later batch analysis and phenotyping of the inflammatory response .

Clinical outcomes: the incidence of death (cardiac and non-cardiac), hospitalizations (for HF, for other cardiac causes not related to HF, for non-cardiac reasons), medications use (number of HF medications, doses) will be recorded at each visit in every patient. Adjudication of events for research purposes will be performed by an *ad hoc* committee blinded to treatment allocation, based on all the data available in the chart including notes, pre-formatted sheets, laboratory and imaging modalities.

6) ENROLLMENT IN THE STUDY

6.1 Screening

Patients will be screened through one of the following routes:

- Patients admitted to the main VCUHealth hospital in Richmond, VA

Our hospital receives >1000 hospitalizations per year for acute decompensated systolic heart failure, of which, we anticipate approximately 30 per month (~36%) will be preliminary eligible for REDHART2 participation. These subjects may be identified by multiple means: direct patient contact by the co-PIs or one of the co-investigators during their regular clinical practice, referral to the research team by coworkers or by the HF Navigator Nurse (a program set to establish post-discharge follow up care for patients), manual screening of the new daily admission list on the electronic medical record by research team, and an automatic alert system generated by the electronic medical record that identifies all new cases that meet pre-specified criteria (i.e., receiving intravenous diuretics, BNP>200 ng/mL, edema on chest radiography). We have been using these strategies for clinical enrollment over the past 3 years. While the system may not be specific (many false positive alerts – screen failures) it is very sensitive with virtually no HF-patient being lost to evaluation.

- Patients admitted to neighboring hospitals in Virginia

Being the only academic medical center in Central Virginia we receive a large number of referrals for inpatient transfers or for outpatient evaluations, i.e., after acute decompensation, especially in underserved population such as the uninsured. In the

recent years, VCUHealth has partnered with the Community Memorial Hospital in South Hill, VA (a 200-bed hospital in the southern corridor of I-85) and with the Virginia Medical Group in Colonial Heights, VA (including a specialized cardiac center with 7 specialists).

- Post-hospital discharge clinics

We have implemented a dedicated clinic for heart failure patients to be seen in clinic within 1 week of hospital discharge as part of the HF Navigator program. This clinic is staffed by a nurse practitioner and a nurse, and supervised by a HF specialist. The research team has access to the daily scheduling list and thus has access to those patients that may have been missed during hospitalization or that may be following up after hospitalization at a different hospital.

6.2 Inclusion Criteria

All 6 criteria need to be met for enrollment of the patient in the study

1. Primary diagnosis for hospitalization is decompensated heart failure established as the finding at admission of both conditions listed below:
 - dyspnea or respiratory distress or tachypnea at rest or with minimal exertion;
 - evidence of elevated cardiac filling pressure or pulmonary congestion (at least one of the conditions must be met):
 - pulmonary congestion/edema at physical exam OR chest X-Ray;
 - plasma BNP levels ≥ 200 pg/mL or proBNP ≥ 600 pg/ml;
 - invasive measurement of left ventricular end-diastolic pressure > 18 mmHg or of pulmonary artery occluding pressure (wedge) > 16 mmHg.
2. The patient has a prior documentation of impaired left ventricular systolic function (ejection fraction $\leq 40\%$) at most recent assessment by any imaging modality (within 12 months).
3. The patient is now clinically stable, euvolemic, and meets standard criteria for hospital discharge as documented by all the 3 conditions listed below:
 - absence of dyspnea or pulmonary congestion/distress at rest;
 - absence of pitting edema in the lower extremities, or in any other region;
 - stable hemodynamic parameters (blood pressure, heart rate).
4. The patient is of age ≥ 21 years old, and is willing and able to provide written informed consent.
5. The patient is willing and able to comply with the protocol (i.e., self-administration, or exercise test).
6. The patient has screening high sensitivity plasma C-reactive protein levels (hsCRP) > 2 mg/L.

6.3 Exclusion Criteria

Subjects will not be eligible if they meet any one of the following 15 exclusion criteria.

1. The primary diagnosis for admission is NOT decompensated heart failure, including

- diagnosis of acute coronary syndromes, hypertensive urgency/emergency, tachy- or brady-arrhythmias.
- 2. Concomitant clinically significant comorbidities that would interfere with the execution or interpretation of the study including but not limited to acute coronary syndromes, uncontrolled hypertension or orthostatic hypotension, tachy- or brady-arrhythmias, acute or chronic pulmonary disease or neuromuscular disorders affecting respiration.
- 3. Cardiac resynchronization therapy (CRT) during index hospitalization, or planned CRT or valve surgeries within the following 6 months.
- 4. Previous or planned implantation of left ventricular assist devices or heart transplant.
- 5. Chronic use of intravenous inotropes.
- 6. Recent (<14 days) use of immunosuppressive or anti-inflammatory drugs (including oral corticosteroids at a dose of prednisone equivalent of 0.5 mg/kg/day but not including inhaled or low dose oral corticosteroids or non-steroidal anti-inflammatory drugs).
- 7. Chronic inflammatory disorder (including but not limited to rheumatoid arthritis, systemic lupus erythematosus).
- 8. Active infection (of any type), including chronic/recurrent infectious disease (i.e. HBV, HCV, and HIV/AIDS) – but excluding HCV+ with undetectable plasma RNA.
- 9. Evidence of COVID19 within the last 60 days or recent (21 days) exposure to close personal contact.
- 10. Current malignancy (excluding carcinoma in situ [any location] or localized non-melanoma skin cancer) receiving targeted therapy
- 11. Any comorbidity limiting survival or ability to complete the study.
- 12. Stage V kidney disease or on renal-replacement therapy.
- 13. Neutropenia (<1,500/mm³ or <1,000/mm³ in African-American patients).
- 14. Pregnancy.
- 15. Angina, hypertension, arrhythmias, electrocardiograph (ECG) changes, or other non-cardiac limitations (i.e., peak respiratory exchange ratio VCO₂/VO₂ [RER]<1.0, reflecting sub-maximal test) that limit maximum exertion during CPX obtained during the baseline testing.
- 16. Hypersensitivity to Kineret or to E. coli derived products.

6.4 Alternate Consent Group

The subjects who are eligible to enroll in the study but decline to participate will be asked to sign an alternate consent that allows the research team to access the electronic health record for 6 months after the enrollment and make one follow up telephone call at the end of the 6 months period if needed to ascertain vital status and incidence of new event. This alternate consent group will provide an estimate of the event rate in a group free of other research interventions.

7) STUDY DESIGN

[figure not shown]
We designed a single center, placebo-controlled, double-blinded randomized study of Anakinra in patients with recently decompensated systolic heart failure. Patients will undergo baseline clinical assessment, CPX, echocardiogram, non-invasive hemodynamics, and blood tests for biomarkers. The CPX, the echocardiogram, non-invasive hemodynamics and blood tests will be repeated at each visit (6, 12 and 24 weeks). See Schematic of Study Design.

7.1 Clinical Assessment

A physician on the research team will conduct a thorough clinical assessment and review of the chart at time of enrollment to evaluate for all inclusion and exclusion criteria. Some of the information needed to determine eligibility may be missing, in which case additional testing would not be performed prior to consenting, and it would be completed only after the patient provided informed consent and it would be charged to the study charge account.

A clinical evaluation will also be completed at Visit 1.5 (14±3 days) to determine tolerability of the treatment and side effects, medication reconciliation and completion of a complete blood cell count with differential and basic metabolic panel.

Visits 2 (6±1 weeks), 3 (12±1 weeks) and 4 (24±2 weeks) will include a clinical safety evaluation as well as assessment of the endpoints. Additional visits may be scheduled as needed.

7.2 Randomization and Allocation Concealment

Randomization will be handled by the investigational pharmacy using a dedicated randomization algorithm. Access to randomization log will be restricted and allowed only on an emergency basis, or as requested by the Data Safety and Monitoring Board (DSMB), or at the end of the study after event adjudication and the database has been locked.

In case of an emergency, a physician treating any patient enrolled in the study may request un-blinding of that individual patient if the physician determines that un-blinding is necessary to make a treatment decision. The PI will contact the VCU Investigational Pharmacy to provide the treatment allocation to the PI, who will then relay the information to the treating physician. If requested by the DSMB, the PI will contact the VCU Investigational Pharmacy to provide the randomization log directly to the DSMB.

Upon completion of the study (including completion of all data collection and event adjudication), the PI will request the complete randomization log from the VCU Investigational Pharmacy. The investigators will also be kept blinded on all inflammatory biomarkers by limiting access to results if obtained during the study (i.e., CRP) and by analyzing all other markers (i.e., cytokines) in a single-batch at the end of the study.

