8.1 Specification of Safety Parameters

Safety parameters will include data deriving from history and physical examination performed at each visit, laboratory data and results of functional and imaging tests. To enhance detection of adverse events between visits, all patients will be encouraged to

contact the research team at any time with concerns or any perceived changes in their healthcare status.

Disease-related data (HF-related) will be assessed including changes in symptoms (or new symptoms), functional capacity, vital signs (including weight), renal function, or any significant changes in medications.

Data specific to the treatment will also be assessed. The patient will be asked about symptoms and examined for signs of infection. Considering that Anakinra may mask signs of infection such as fever, a low threshold for further investigation will be advocated. A complete cell count will be measured at each visit to exclude the unusual cases of Anakinra-related neutropenia (ANC<1000), for which suspension of active treatment will be considered until return to a value of ANC>1,800/mm³ (or >1,000/mm³ if patient is African-American). Cessation of Anakinra will not be mandatory. Changes to treatment for side-effects or unanticipated problems will be performed without breaking the randomization code, unless deemed necessary for the treatment of the individual patient by the physician, in which case the physician will be made aware while the remainder of the team, especially the investigators performing and interpreting the tests, will be maintained blinded. The risks of the tests performed have been described above. In order to reduce risk, the procedures will be performed by skilled practitioners in the standard clinical fashion. Abnormal or incidental findings will be handled on a case by case basis as clinically indicated.

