8.4 Reporting Procedures

8.4.1 Serious Adverse Events

All unexpected AEs that result in death or are otherwise reportable SAEs or AEs will be reported promptly to the Data Safety Monitoring Board (DSMB) and the IRB within 1 business day of investigators becoming aware of the event. AEs (serious or non-serious) that transpire secondary to an overdose must also be reported to the DSMB within 1 business day of knowledge of the event, using an AE form. The SAE form will always be completed as thoroughly as possible with all available details of the event, signed by the investigator (or designee), and, if a reportable adverse event as defined herein, forwarded to the DSMB within the designated time frames. If the investigator does not have all information regarding an SAE, he/she will not wait to receive additional information before notifying the DSMB of the event and completing the SAE form. The form will be updated when additional information is received. The investigator will always provide an assessment of causality at the time of the initial report.

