9.1 Event-adjudication committee

The event-adjudicating committee will be composed of professionals from different backgrounds including general cardiologists, cardiologists with training in heart failure, general internal medicine specialists, emergency medicine specialists, and infectious disease specialists. Each event will be reviewed by at least 3 members. Agreement will be necessary for all 3 members, disagreement will be resolved with discussion of the case, followed by voting of at least 5 members if disagreement remains. The committee will meet at the end of the study and review all adjudicated events. The committee will be blinded to treatment allocation. In order to favor allocation concealment, the committee will also be blinded to C-reactive protein levels, which may be affected by treatment.

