10.1 Reasons for Discontinuation of Treatment or Withdrawal from the Study

Patients may withdraw from the study at any time. The investigators may temporarily suspend treatment at any time in patients experiencing an adverse event considered possibly, probably, or definitely related to the study drug. The study drug may then be restarted upon resolution of the adverse event unless the adverse event is considered likely to reoccur or the patient is unwilling to restart treatment. The investigators can withdraw any patient at any time from the study if medically necessary. It will be extremely important to obtain complete follow-up data on each patient, except on those who withdraw consent to release such information. It will be documented whether or not each patient completed the study. If for any reason the study treatment or observations were discontinued, the reasons will be recorded and the IRB will be informed.

Reasons for discontinuation of Anakinra (or placebo):

- 1) Systemic infection (sepsis)*;
- 2) Surgery*;
- 3) New diagnosis of cancer that requires local or systemic treatment;
- 4) Hypersensitivity reaction (rash, anaphylaxis, arthritis);
- 5) Severe injection site reactions*;
- 6) Need for immunosuppressant therapy;
- 7) Acute myocardial infarction or stroke*;
- 8) Severe neutropenia (<1,000/mm³) if there is a perception of increased infectious risk by the provider*.

* treatment may be restarted by investigators after the condition is resolved

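### Section 7.2 gives the PI the patient's allocation at every emergency unblinding, although section 8.1 keeps everyone but the physician blinded

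*Combined protocol and SAP*

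**What the plan says.** Section 7.2 opens the emergency route to any treating doctor: "a physician treating any patient enrolled in the study may request un-blinding of that individual patient". The PI then contacts the investigational pharmacy "to provide the treatment allocation to the PI, who will then relay the information to the treating physician". The next sentence of 7.2 deals with requests from the DSMB differently: "the PI will contact the VCU Investigational Pharmacy to provide the randomization log directly to the DSMB". There the PI passes on the request but does not receive the answer.

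Section 8.1 covers treatment changes for side effects or unanticipated problems. They are to be made without breaking the code unless the physician considers a break necessary for that patient. In that case "the physician will be made aware while the remainder of the team, especially the investigators performing and interpreting the tests, will be maintained blinded".

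Investigators keep a working role after such an event. Section 8.4.1 states "The investigator will always provide an assessment of causality at the time of the initial report". Section 10.1 lets investigators suspend and restart study drug after a related adverse event, and adds "The investigators can withdraw any patient at any time from the study if medically necessary". Under section 10.3 the co-PIs meet monthly to discuss enrolment, withdrawals and adverse events.

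**The concern.** The two sections give different answers to the question of who may know the arm after a code break. Site staff cannot follow both unless the PI happens to be the physician who needs the information.

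What is at stake is the blinding of safety judgements on that patient. Under sections 8.3.1 and 8.3.2, whether an event counts as an AE or SAE at all depends partly on whether the investigator regards it as expected from the underlying disease. Causality, and the decision to suspend, restart or withdraw, are also matters of opinion. Knowing the arm can influence each of them. The patient meanwhile stays in the trial: section 10.2 offers all functional assessments even to those who have stopped injections, for the intention-to-treat analysis.

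The plan plainly values investigator blinding, since 7.2 restricts investigators' access to CRP results obtained during the study. Handing the actual allocation to a PI sits badly with that.

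**Working it through.** No arithmetic decides the point. The check is to compare the sections.

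1. **Who learns the arm.** Under 7.2 the information goes from pharmacy to PI to treating physician, so two people outside the pharmacy learn it. Under 8.1 only the physician does. The difference is one person, the PI, and it disappears only if the PI is that physician.

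2. **Whether the sections describe the same act.** 8.1 speaks of side effects and unanticipated problems, 7.2 of emergencies. Both concern breaking one patient's code because that patient's treatment requires it. An emergency caused by a suspected side effect falls under both.

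3. **Whether anything reconciles them.** I found no sentence in 7.2, 8.1, 8.6, 10.1 or 10.3 that exempts the PI from the team to be kept blinded, or that takes an unblinded PI out of later judgements on the patient. The Key Personnel table lists two PIs, and 7.2 does not say which one receives the allocation.

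4. **Whether the relay is needed.** The DSMB route in 7.2 already separates asking from receiving. The PI contacts the pharmacy, and the pharmacy delivers to the requester. The same separation would work for a treating physician.

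5. **What is exposed.** AE and SAE classification (8.3.1, 8.3.2), causality (8.4.1), and suspension, restart or withdrawal (10.1), for the unblinded patient.

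6. **What is protected.**
   - Raw exercise data go without identifiers to an outside core laboratory (7.4), which analyses them by coded group (11.3.3).
   - Echocardiograms are measured at the end of the study by two blinded operators (7.5).
   - On events, section 9.1 states "The committee will be blinded to treatment allocation", and the committee does not see CRP either.
   - The documents give the PI no stated role in running or reading the tests.

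7. **How many patients.** The documents give no expected number of requests. As an assumption, 1% to 5% of 102 patients gives 0.01 × 102 = 1.02 and 0.05 × 102 = 5.1, or about 1 to 5 patients.

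**The case against.** The strongest reply is that this is ambiguity, not contradiction. The physician in 8.1 can be read as a study physician adjusting treatment, with 7.2 covering a request from any doctor, possibly outside the team. On that reading the common aim is to shield those who run and read the tests, and the PI is not named as one of them. A PI contact point is also a sensible gatekeeper, because patients may come from neighbouring hospitals (section 6.1) and the pharmacy may not know the caller.

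Part of this stands. The gatekeeper argument is fair, and the fix should keep that function. It justifies the PI in passing on the request, though, not in receiving the answer. The narrower reading of 8.1 does not remove the conflict: the section singles out the test investigators for emphasis but applies to the whole remaining team.

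The objection also rightly limits the consequences. A reader might infer that the primary endpoint is compromised because later exercise tests fall under a team whose lead knows the arm. The documents do not support that, given the safeguards in sections 7.4, 7.5, 9.1 and 11.3.3 and the absence of any PI role in testing. A reader might also infer that a revealed arm lets the PI guess other patients' arms from side-effect patterns. That is speculation: each disclosure covers one patient, and section 8.3.1 already describes injection site reactions in up to 50% of treated patients, so one more known case adds little.

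The safeguards are not complete. Adjudicators work from chart notes and pre-formatted sheets (5.2), investigators record and diagnose suspected events (8.5), and coded analysis does not protect judgements made before the data reach it.

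**Conclusion.** The conflict is real. Following 7.2 breaches 8.1 at each emergency request, except where the PI is the physician who needs the allocation. The effect is modest and confined to investigator safety and treatment-continuation judgements on the individual unblinded patient. The primary endpoint and adjudicated events are largely protected.

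The number affected is probably small. The figure of 1 to 5 patients rests entirely on the assumed 1% to 5% request rate, and no effect on bias or power has been shown. The conclusion also assumes that the PI belongs to the team that 8.1 keeps blinded, which is the natural reading because nothing exempts the PI. It is worth correcting because the change is cheap and the plan already contains the better route.

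**What to change.** Amend section 7.2 to match 8.1 and the existing DSMB route:

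- The PI or a delegate may forward or authorise the request.
- The pharmacy gives the allocation directly to the requesting treating physician and logs the disclosure.
- The PI is told only that unblinding took place.
- If a PI is the treating physician and so learns the arm, a blinded co-investigator makes later causality and AE/SAE classification judgements for that patient where feasible.

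This will not bring PI exposure to zero, because the last case remains. It changes who receives information and leaves the physician's access and every treatment rule as they are.

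The cost is a short rewording of 7.2, plus a pharmacy procedure for reaching and verifying the requesting physician. That procedure is the one practical burden, mainly for doctors at outside hospitals.
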